8.5.3. Physical Examination

Physical examinations will be conducted by a physician, trained physician’s assistant, or nurse practitioner as acceptable according to local regulation at visits specified in the Schedule of Activities in Section 8.11 (see also Section 8.1, “[Timing of Assessments](#)”). Height and weight will also be measured at visits specified in the Schedule of Activities in Section 8.11. The person conducting the physical examination will document this in the subject’s medical records. Clinically significant abnormal findings should be recorded as AEs.

Particular attention should go to physical examination at all visits, to identify any potential SARS-CoV-2 related signs and symptoms, indicating potential infection (e.g. cough, fever, headaches, fatigue, dyspnea, myalgia, anosmia, dysgeusia, anorexia, sore throat, others). Subjects

presenting such symptoms at screening/baseline should not be included/randomized in the study (see Section 6.2). Developing such symptoms during the study, should be managed as per Section 8.5.6.

8.5.4. Vital Signs

Vital signs (systolic and diastolic blood pressure taken at the same arm for each measurement, pulse and oral/tympanic body temperature, the same method of measuring body temperature to be used throughout the study) will be recorded in a standardized manner (i.e. after the subject has rested in a supine position for at least 5 minutes) at visits specified in the Schedule of Activities in Section 8.11 (see also Section 8.1, “Timing of Assessments”). Clinically significant abnormal values should be recorded as AEs.

8.5.5. 12-lead Electrocardiogram

At the time points specified in the Schedule of Activities (see Section 8.11 and also Section 8.1, “Timing of Assessments”), a triplicate 12-lead ECG will be recorded and results will be sent for central reading.

12-lead ECG recordings will be performed before blood sampling and after subjects rested for at least 5 minutes in supine position. In case an indwelling catheter is used, ECGs may be recorded after blood sampling, provided that there is at least 30 minutes between catheter insertion and the ECG recording. When catheter insertion would fail, the 12-lead ECG needs to be taken before the venipuncture and at least 30 minutes after the failed attempt. Triplicate ECGs will be performed within a time span of 10 minutes, with an approximate 3-minute interval between ECGs.

The following parameters need to be recorded: heart rate, RR interval, PR interval, QRS interval, uncorrected QT interval, morphology and rhythm analysis (QTcF will be derived). QTcF will be considered as normal if ≤ 450 ms (male) and ≤ 460 ms (female), while a prolongation of QTcF to > 500 ms or an increase from baseline > 60 ms will be considered a threshold of concern.

Immediately after recording, the ECG will be reviewed by the investigator on clinical significant abnormalities. This immediate review during the visit needs to be documented in the subject’s source. After receipt of the central report, also all flagged ECG abnormalities need to be assessed by the investigator on clinical relevance. Clinically significant abnormal findings should be recorded as AEs.

8.5.6. Other Safety Assessments

SARS-CoV-2 infection will be assessed at screening by RT-PCR and at baseline through careful physical examination to exclude any potential signs and symptoms of infection, e.g. cough, fever, headaches, fatigue, dyspnea, myalgia, anosmia, dysgeusia, anorexia, sore throat, etc.

Additional RT-PCR and serology testing will be repeated at baseline for documentation and throughout the study as needed. The subject could be tested for SARS-CoV-2 in facilities outside the study site and if so, the subject should be instructed to immediately inform the study

investigator if the test is positive and test results should be shared with the investigator as soon as possible.

On Day 8, subjects should be contacted by the site via a telephone call. The site should remotely check the overall status of the subject and review safety related information, if applicable, both in the context of the clinical study and linked to the SARS-CoV-2 pandemic.

8.6. Pharmacokinetic Assessments

Blood samples for the PK assessment of GLPG3970 should be collected on the visits specified in the Schedule of Activities in Section 8.11 (see also Section 8.1, “Timing of Assessments”).

Samples will be obtained by venipuncture (or indwelling cannula), preferably in the forearm into tubes containing K2EDTA and will be immediately chilled (ice bath). Within 30 minutes after blood collection, the plasma will be separated in a refrigerated centrifuge at 4 °C for 10 minutes at circa 1500 g and transferred into tubes as described in the laboratory manual. The plasma samples will be stored at -60 °C or below at the site until shipment to the bioanalytical laboratory.

A high-contrast, black and white image showing a series of horizontal bars of varying lengths and positions. The bars are composed of black pixels on a white background. The top bar is the longest and is positioned near the top of the frame. Below it are several shorter bars of varying widths, some with small black squares to their left. The bars are arranged in a staggered, non-overlapping pattern across the frame.

8.8. Other Assessments

Not applicable.

8.8.1. Subject Diary

At visits specified in the Schedule of Activities (Section 8.11) a diary and instructions for completion will be provided. The subjects will record on a daily basis any changes in concomitant illnesses, new AEs, exposure to individuals with confirmed or suspected diagnosis of SARS-CoV-2 infection, any change in concomitant medication, date and time of IP and MTX intake, and whether IP intake was done on an empty stomach (i.e. 1 hour prior and at least 2 hours after a meal) throughout the study (from signature of ICF until the FU visit). An automated alert system will notify the investigator and sponsor of any signs or symptoms or information possibly related to SARS-CoV-2 that is entered by the subject in the diary.

Subjects will be trained on how to complete the subject diary.

8.9. Sample Management

The total amount of blood to be taken per subject over a period of 11 weeks, for scheduled safety laboratory parameters and PK [REDACTED] assessments, will not exceed approximately [REDACTED] mL.

Blood and Urine Samples for Routine Safety Tests, Serology, FSH and Pregnancy Tests

All blood and urine samples for routine safety tests, serology, FSH and pregnancy tests will be analyzed in a central laboratory and will be destroyed after analysis.

Blood Samples for PK and [REDACTED]

After the end of the study (defined in Section 5.2), all biological samples obtained during the clinical study may be stored for a maximum period of 5 years, after which the samples will be destroyed. The sample storage period will be in accordance with the IRB/EC-approved ICF and applicable laws (e.g. health authority requirements).

The stored samples shall only be used by the sponsor, sponsor partners and/or other companies contracted by the sponsor, for research related to this clinical study. Any research outside the context described in this CSP may only be conducted after approval by the IRB/IEC and Regulatory Authority and after obtaining informed consent from the subject.

8.10.

8.11. Schedule of Activities

For detailed instructions on the clinical study procedures, please see referred sections and Section 8.1, “[Timing of Assessments](#)”.

EVENT	SCREENING PERIOD	TREATMENT PERIOD ^{1,2}						FOLLOW-UP PERIOD ²
		1	2	3	4	5	ED ³	
Study visit	S	1						FU Visit
Study Weeks		Baseline	1	2	4	6		
Study Day (D) ± Days	-21 to -1	1	8 ± 2	15 ± 2	29 ± 2	43 ± 2	Early treatment discontinuation	57 ± 3
On site visit	✓	✓		✓	✓	✓	✓	✓
Telephone call			✓					
Informed consent	✓							
Inclusion/exclusion criteria	✓	✓						
Demographics	✓							
Medical history	✓							
FSH test (postmenopausal women)	✓							

¹ On dosing days, all assessments are to be performed within 3 hours pre-dose, unless otherwise specified.

² Subjects must come for the study visits 1, 3 and 5 in the morning in a fasting state (no food intake for at least 8 hours). For Visit 1 (predose measurements) and for 2 post dose visits (Visit 3, 4 or 5) all attempts should be made to plan the visit within 2 days following MTX intake.

³ Subjects who discontinue treatment early will be requested to return for an early discontinuation (ED) visit to complete all Visit 5 assessments and to return for a follow-up (FU) visit 14 ± 3 days after last IP administration.

EVENT	SCREENING PERIOD	TREATMENT PERIOD ^{1,2}						FOLLOW-UP PERIOD ²
		1	2	3	4	5	ED ³	
Study visit	S	1						FU Visit
Study Weeks		Baseline	1	2	4	6		
Study Day (D) ± Days	-21 to -1	1	8 ± 2	15 ± 2	29 ± 2	43 ± 2	Early treatment discontinuation	57 ± 3
Pregnancy test ⁴	✓	✓			✓	✓	✓	
Physical examination	✓	✓				✓	✓	✓
Vital signs	✓	✓		✓	✓	✓	✓	✓
Body weight and height ⁵	✓	✓		✓	✓	✓	✓	✓
12-lead triplicate ECG	✓	✓		✓	✓	✓	✓	✓
Serology	✓							
QuantiFERON-TB Gold test	✓							
SARS-CoV-2 RT-PCR test ⁶	✓	✓	As needed					
SARS-CoV-2 serology test ⁶		✓	As needed					
Randomization		✓						
Clinical safety blood samples	✓	✓ ⁷		✓ ⁷	✓	✓ ⁷	✓	✓

⁴ Serum beta human chorionic gonadotropin at screening, baseline (Visit 1), Visit 4 and Visit 5, or at the ED visit, if applicable (all female subjects).

⁵ Height only to be measured at screening.

⁶ RT-PCR from a nasal swab sample at screening and RT-PCR from a nasal swab sample and serology testing at baseline (Visit 1), and as needed when subject presents signs and symptoms of SARS-CoV-2 infection.

⁷ Fasted glucose, fasted insulin and HOMA-IR only at Visit 1, 3 and 5 and the ED visit, if applicable.

EVENT	SCREENING PERIOD	TREATMENT PERIOD ^{1,2}						FOLLOW-UP PERIOD ²
Study visit	S	1	2	3	4	5	ED ³	FU Visit
Study Weeks		Baseline	1	2	4	6		
Study Day (D) ± Days	-21 to -1	1	8 ± 2	15 ± 2	29 ± 2	43 ± 2	Early treatment discontinuation	57 ± 3
Clinical safety urine samples ⁸	✓	✓ ⁹		✓	✓	✓ ⁹	✓	✓
PK blood samples for GLPG3970		✓ ¹⁰		✓ ¹¹	✓ ¹¹	✓ ^{11,12}	✓	
		█		█	█			
		█		█		█	█	█
		█		█		█	█	
		█				█	█	
Subject diary evaluation		✓	✓	✓	✓	✓	✓	✓

⁸ On dosing days, clinical safety urine samples will be taken predose, on the same visit day.

⁹ Visit 1 and 5: predose and 2 hours postdose. Calcium and phosphate should only be evaluated at Visits 1 and 5.

¹⁰ Visit 1: predose (within 30 minutes prior to dosing), 1 sample within [0.5-1.5 hours postdose] and 1 sample within [2 – 2.5 hours postdose].

¹¹ Visit 3, 4 and 5: predose (within 30 minutes prior to dosing).

¹² Visit 5: 1 sample within [4-6 hours postdose].

13

EVENT	SCREENING PERIOD	TREATMENT PERIOD ^{1,2}						FOLLOW-UP PERIOD ²
		1	2	3	4	5	ED ³	
Study visit	S	1						FU Visit
Study Weeks		Baseline	1	2	4	6		
Study Day (D) ± Days	-21 to -1	1	8 ± 2	15 ± 2	29 ± 2	43 ± 2	Early treatment discontinuation	57 ± 3
SJC66/TJC68	✓	✓		✓	✓	✓	✓	
	█	█		█	█	█	█	
	█	█	█	█	█	█	█	
Dispense IP		✓ ¹⁵		✓ ¹⁵	✓ ¹⁵			
IP administration ¹⁵		Once daily throughout the treatment period						
AE and concomitant medication		throughout the study						

¹⁵ On Visit 1, 3, 4 and 5 administration of IP must occur at site.

9. STATISTICAL METHODS

All statistical methods shall be detailed in a statistical analysis plan (SAP) that will be finalized prior to the database lock and unblinding. All relevant data collected in this clinical study will be documented using summary tables, figures, and subject data listings.

Any deviations from the CSP are to be justified in the SAP.

[figure not shown]
9.1. Determination of Sample Size

The operating characteristics of the chosen decision framework at a sample size of 15 subjects (GLPG3970) + 10 subjects (placebo) are represented in the following graphical output and table, and were deemed acceptable. A common standard deviation (SD) of 1.3 for placebo and GLPG3970 was assumed based on previous experience with RA studies.

Lower Reference Value and Target Value for the decision framework were determined based on the published studies and the therapies in development or on the market. They were identified by the project team as the lowest delta of possible interest and the best case scenario for efficacy outcome respectively.

A dropout rate of 20% was taken into account to allow a minimum of 20 subjects to complete the study. In case of drop-outs due to SARS-CoV-2 infection, additional subjects may be randomized on top of the planned sample size. The number of additional subjects randomized will not exceed the number of subjects dropping out of the study in relation to SARS-CoV-2. Randomization of additional subjects will ultimately be decided by the sponsor before any study lock or related unblinding has occurred.

Probability	Reference value	Outcome
0.852	-1.6	Signal detected
0.043	-1.6	No conclusion
0.105	-1.6	No signal detected
0.192	-0.6	Signal detected
0.091	-0.6	No conclusion
0.717	-0.6	No signal detected

9.2. Population for Analyses

9.2.1. All Screened Subjects

All subjects who signed and dated an ICF.

9.2.2. All Randomized Subjects

All screened subjects who were randomized into the clinical study.

9.2.3. Full Analysis Set

All randomized subjects who have received/used at least 1 dose of IP.

9.2.4. Safety Analysis Set

All subjects who used at least 1 dose of IP.

9.2.5. Pharmacokinetic Analysis Set

Subset of the Safety Analysis Set for which plasma concentration data are available to facilitate development of the Population PK model as described in the pharmacometric analysis plan and excluding CSP deviations which have an impact on the PK analysis.

9.2.6. [REDACTED]

[REDACTED]

[REDACTED]

9.2.7. Pharmacokinetic/ [REDACTED]

Intersection of the PK and [REDACTED].

9.3. Statistical Analyses

9.3.1. General Statistical Considerations

Summary tabulations will be presented and will display the number of observations, mean, SDs and/or standard error (as appropriate), median, minimum and maximum (for continuous variables), and the number and percentage per category (for categorical data). In addition to tabulated descriptive statistics, graphical data displays may be used to summarize the data.

Baseline is defined as the last available assessment prior to the first intake of IP. For ECG, the baseline ECG result is the mean of the last available triplicate prior to the first intake of IP.

Unless otherwise noted, inferential statistics will be interpreted at the 2-sided 10% significance level. Data may be pooled across centers and countries.

9.3.2. Interim Analysis

No formal interim analysis is planned for this clinical study.

9.3.3. Analyses of Demographics and Baseline Characteristics

Subject disposition (including reasons for ED), CSP deviations, demographics, baseline characteristics, medical history, and concomitant therapies will be analyzed descriptively

9.3.4. Analyses of Efficacy Parameters

Efficacy analyses will be performed on the Full Analysis Set.

9.3.4.1. Analysis for Primary Efficacy Endpoint

A mixed model for repeated measures (MMRM) will be used on the DAS28 (CRP) changes from baseline to compare treatment groups, with a 90% confidence interval (CI) of the treatment difference at Week 6.

Secondly, the signal detection methodology described by Frewer et al (Frewer, Mitchell, Watkins, & Matcham, 2016) will be used to provide further insight into the treatment effect of GLPG3970 over placebo, and will support scenario analyses. The posterior distribution of this treatment effect will be estimated, and from this distribution probabilities of reaching at least a certain effect (delta) will be derived, e.g. a range of plausible effect size values going from as high as $P(\delta \leq -1.6)$ to as low as $P(\delta \leq -0.6)$.

The chosen framework is as follows:

- Target value (TV): -1.6 and lower reference value (LRV): -0.6
- False stop risk: 20% and false go risk: 10%
- Framework rules:
 - o Signal detected if $P_{10} < TV$ and $P_{80} < LRV$
 - o No signal detected if $P_{10} \geq TV$
 - o No conclusion if $P_{10} < TV$

9.3.4.2. [REDACTED]

[REDACTED]

[REDACTED]

[REDACTED]

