6.2.2.3. Decision Making Methodology

The decision making methodology described by Frewer et al (Frewer, Mitchell, Watkins, & Matcham, 2016) will be used to provide further insight into the treatment effect of GLPG3970 over placebo, and will support scenario analyses. The posterior distribution of this treatment effect will be estimated, and from this distribution probabilities of reaching at least a certain effect (delta) will be derived, e.g. a range of plausible effect size values going from as high as P ($\delta \leq -1.6$) to as low as P ($\delta \leq -0.6$).

The chosen framework parameters are as follows:

[figure not shown]
- TV: -1.6 and LRV: -0.6
- False stop risk: 10% and false go risk: 20%
- Framework rules:
 - o Signal detected if $P10 < TV$ and $P80 < LRV$
 - o No signal detected if $P10 \geq TV$
 - o No conclusion if $P10 < TV$

More details about this analysis will be provided in a separate document. This output will be generated for decision making purposes and will not be part of the CSR.

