6.7. Changes to the Planned Analyses, Not Covered by Protocol Amendments

Not applicable.

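### The Protocol swaps the false-stop and false-go risks, and in both documents the No conclusion rule also covers every Signal detected result

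*Protocol*

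**What the plan says.** Both documents add a three-outcome decision framework to the mixed model for repeated measures (MMRM) for the primary endpoint. It uses the posterior distribution of the GLPG3970-minus-placebo difference in DAS28 (CRP) change at Week 6. The anchors are "Target value (TV): -1.6 and lower reference value (LRV): -0.6" (Protocol 9.3.4.1), and SAP 6.2.2.3 has the same values.

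The stated error risks differ:
- Protocol 9.3.4.1: "False stop risk: 20% and false go risk: 10" per cent.
- SAP 6.2.2.3: "False stop risk: 10% and false go risk: 20" per cent.

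The rules are the same in both documents:
- Signal detected: P10 below TV and P80 below LRV.
- No signal detected: P10 at or above TV.
- No conclusion: P10 below TV. The Protocol line reads "No conclusion if $P_{10} < TV" and sets no condition on P80. The SAP line has the same content.

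The same operating-characteristics table is printed in Protocol 9.1 and SAP 2.6. Protocol Section 9 requires deviations from the protocol to be justified in the SAP. SAP 6.7, "Changes to the Planned Analyses, Not Covered by Protocol Amendments", is answered as not applicable.

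**The concern.** There are two separate faults.

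**Swapped risks.** The percentile in each rule fixes the error risk. Stopping when P10 ≥ TV gives a false-stop risk of 10% at TV, and requiring P80 < LRV for a signal gives a false-go risk of 20% at LRV. The Protocol assigns these figures the other way round. It contradicts its own rules and table, and it contradicts the SAP. A reader who takes the Protocol's label at face value believes that the chance of advancing a drug whose true effect is only the LRV is half what it is.

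**Overlapping outcomes.** The condition for No conclusion is one of the two conditions for Signal detected. Any result that qualifies as a signal therefore also qualifies as no conclusion, and the written rule does not give one decision for a positive result.

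The framework's operating characteristics are the stated justification for 15 + 10 subjects, and the SAP says the output serves decision making. The prespecified text should therefore give one outcome per result and state its error risks correctly.

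**Working it through.** **Inputs.** TV = -1.6 and LRV = -0.6 (Protocol 9.3.4.1, SAP 6.2.2.3); common SD 1.3 and 15 + 10 subjects (Protocol 9.1, SAP 2.6). Two assumptions are added: P10 and P80 are the 10th and 80th posterior percentiles of the difference, and the posterior is normal with a flat prior. The documents state no prior.

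**Cut-offs.** Let d be the observed difference.
- SE = 1.3 × √(1/15 + 1/10) = 0.531
- P10 = d - 1.2816 × SE, so P10 < TV when d < -1.6 + 1.2816 × 0.531 = -0.920
- P80 = d + 0.8416 × SE, so P80 < LRV when d < -0.6 - 0.8416 × 0.531 = -1.047

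The P80 cut-off is the stricter one, so at this sample size a signal needs d < -1.047.

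**Reproducing the plan's table**, with No conclusion taken as P10 < TV and P80 ≥ LRV. Each cell gives signal / no conclusion / no signal.

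| Version | True effect -1.6 | True effect -0.6 |
|---|---|---|
| Table in both documents | 0.852 / 0.043 / 0.105 | 0.192 / 0.091 / 0.717 |
| P10/P80, SD known | 0.851 / 0.049 / 0.100 | 0.200 / 0.073 / 0.727 |
| P10/P80, SD estimated, t quantiles (400,000 simulations) | 0.842 / 0.059 / 0.099 | 0.189 / 0.096 / 0.716 |
| P20/P90, as the Protocol's risks imply, SD known | 0.727 / 0.073 / 0.200 | 0.100 / 0.049 / 0.851 |

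Both P10/P80 versions match all six table entries within 0.02, which supports the two assumptions. The P20/P90 version has cut-offs of -1.153 for P20 < TV and -1.280 for P90 < LRV. It does not match: P(signal) is 0.727 against 0.852 at TV, and 0.100 against 0.192 at LRV. The table was therefore computed with false stop 10% and false go 20%.

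**The third rule read literally** (P10 < TV only, SD known):
- at -1.6: 1 - 0.100 = 0.900, against 0.043 in the table
- at -0.6: 1 - 0.727 = 0.273, against 0.091 in the table

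The plan's own table leads to the same place: 0.852 + 0.043 = 0.895 and 0.192 + 0.091 = 0.283.

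With the literal rule the three outcomes sum to 0.851 + 0.900 + 0.100 = 1.851 at -1.6, and to 0.200 + 0.273 + 0.727 = 1.200 at -0.6. Each set in the table sums to 1, so it was computed with a P80 condition that neither document states.

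**The case against.** The strongest case concerns consequence. The SAP, which the Protocol names as the place for detailed methods, already has the risks in the right order. The Protocol prints the true false-go probability (0.192) in its own table. Because the table's probabilities sum to 1, a careful reader can recover No conclusion as the remaining zone. The MMRM is the first-listed analysis and the framework comes second; its output stays out of the clinical study report, so no reported estimate, interval or p-value changes. A separate document is to give more detail and may state the rule in full. The literal 0.90 and 0.27, and the P20/P90 figures, describe readings that nobody is shown to have used. The SAP's changes section is arguably not the place for a corrected label: the SAP recorded another Protocol slip, the HOMA-IR unit, in its version history.

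Most of this is true, and it limits the damage. It does not make the text correct. Neither document says the rules are applied in order, and order would not cure the swapped risks. The separate document is not part of the plan under review. The label correction appears neither in SAP 6.7 nor in the legible part of the version history, although Protocol Section 9 asks for deviations to be justified in the SAP.

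**Conclusion.** Both faults stand. The Protocol's risks are reversed: the rule and table carry a false-stop risk of about 10% (0.105 in the table, 0.100 recomputed) and a false-go risk of about 20% (0.192 and 0.200), so the stated false-go risk of 10% is about half the real one. The third rule is incomplete in both documents and overlaps fully with Signal detected.

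The figures rest on SD 1.3, 15 + 10 evaluable subjects and a flat-prior normal posterior; estimating the SD changes them little. The sample size, the printed table and the MMRM do not change. The error lies in the written decision rule and its stated risk, and should be closed before unblinding.

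**What to change.** 1. In Protocol 9.3.4.1, set the risks to false stop 10% and false go 20%, in line with the rules, the table and the SAP.
2. In Protocol 9.3.4.1 and SAP 6.2.2.3, complete the third rule so that No conclusion requires P10 < TV and P80 ≥ LRV. The three outcomes are then mutually exclusive and exhaustive, and they correspond to the table.
3. Record both corrections in SAP 6.7, and check that the separate document on the framework uses the same rule.

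The cost is wording only, with no new subjects, data or sample-size work. The Protocol's stated false-go risk becomes less favourable, 20% instead of 10%, but that is the risk the design already carried.
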